## Covariates

The cohort will be divided into two groups at baseline: obese, defined as  $\text{BMI} \geq 30 \text{ kg/m}^2$ , and non-obese, defined as  $\text{BMI} < 30 \text{ kg/m}^2$ . For descriptive purposes and adjusting, we will be using the following pre-TKA exposure covariates: age (years) at the time of TKA, sex (coded as female=1; male = 0), household income (at the year before KA, categorized into quartiles), highest completed education (at the year of KA, categorized into 3 categories: <11, 11 to 15, and >15 years). Comedication (at least one redeemed prescription 365 days earlier to index KA - 60 days for antibiotics): 1) Glucose-lowering due to the association between DM and surgical complications. 2) Antithrombotic medications and 3) NSAIDs because of the possible postoperative bleeding-related complications and 4) Antiresorptives due to the possible increased risk of revision. The last covariate to be included in matching and adjustment is Elixhauser Comorbidity Measure (ECM) (at the year of KA, categorized into 3: 0, 1-2 and  $\geq 3$ ), ECM is validated comorbidity scoring measure that has shown highest discriminative ability for the occurrence of all categories of postoperative adverse outcomes following orthopedic surgeries.

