## Statistical Methods

We will use descriptive statistics to summarize baseline characteristics of the two groups and will compare them using standardized differences. The 2-year (730 days) cumulative incidence of PJI will be reported for both groups. Hazard ratios with corresponding two-sided 95% confidence intervals (CIs) will be estimated using a Cox proportional hazards regression model. We will fit both unadjusted (crude) models and propensity adjusted models using inverse probability of treatment weighting (IPTW). For the adjusted model, propensity scores will be calculated based on age in years, female sex, completed education, household income, comedications, and ECM (all collected prior to surgery). Subsequent stratified analyses will categorize the observed PJI cases by bacterial infection type (within the first 90 days postoperatively or between 91 days and 2 years) and compare crude proportions between groups based on the absolute risk difference with 95% confidence intervals.

[figure not shown]
We present several analyses corresponding to the main results with 95% confidence intervals rather than P values, and comply with 2 Acta Orthopaedica principles for concluding whether scientifically important differences exist:

- A statistically non-significant test is not sufficient to claim "no difference." To show "no difference," a smallest clinically relevant size of the difference (it might be 0) must be defined. If all clinically relevant differences are excluded from the difference's confidence interval, a "no difference" or similarity/comparability conclusion is reasonable.
- A statistically significant test does not necessarily imply a clinically important difference. The importance of the tested null hypothesis depends on the smallest clinically relevant difference that should be defined a priori. If the difference's confidence interval excludes all clinically irrelevant differences, a conclusion concerning the existence of a clinically important difference is reasonable.

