To evaluate imprecision in the estimated treatment effect, a clinically important difference must first be defined. Based on an expected 2-year incidence of PJI of about 1%, a 50% increase in risk would be considered clinically relevant. In a time-to-event analysis, this corresponds to a hazard ratio of 1.5. Accordingly, non-inferiority—or absence of a clinically meaningful increase in risk—will be established if the upper bound of the 95% confidence interval for the hazard ratio remains below 1.5. We will visualize the 2-year cumulative incidence of all outcomes for both groups using the cumulative incidence functions (CIFs).

**Handling of missing data and sensitivity analyses:** Missing data is unavoidable in epidemiological and clinical research and must be explained otherwise it could undermine the credibility and validity of the research results. Missing values, for either predictors or outcomes, occur in all types of medical research. Unless prompted to do otherwise, most statistical packages explicitly exclude individuals with any missing value on any of the data analyzed. The resulting so-called "available case" or "complete case" analysis is the most common "default approach" to handle missing data, although it is rarely justified. Subjects with missing weight or height will be excluded from the analysis. Missingness of data on some of the covariates used for adjusting will be ignored but the subjects will not be excluded. Patients who will be lost during the follow up period (e.g., due to death or migration) are expected to be extremely few and no systematic difference is expected to be seen.

Therefore, this missingness of outcome data will be assumed "Missing completely at random" (MCAR), as there is no evidence to suggest systematic differences between the missing values and the observed values and will be ignored. For the purpose of sensitivity, we will potentially re-do the main analysis where missing outcome data is replaced twice, using best-case imputation ( $y=0$ ; no PJI) and worst-case imputation ( $y=1$ , PJI yes).

[figure not shown]
**Figure 1 (Mockup):** study flow chart

**Table 1 (Mockup).** Baseline characteristics at time of total knee arthroplasty

|  | Obese | Non-Obese | Std. Diff |
|--|-------|-----------|-----------|
| Age, years                                 |       |           |           |
| Female Sex, no. (%)                        |       |           |           |

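### The Elixhauser score enters the propensity score for obesity with no exclusion of an obesity item; if the version used has one, the adjusted hazard ratio is likely pulled down

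*Combined protocol and SAP*

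**What the plan says.** All references are to the combined protocol and SAP.

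- **Exposure (Covariates).** "The cohort will be divided into two groups at baseline": BMI of 30 kg/m² or more, and BMI below 30.
- **ECM as covariate (Covariates).** "The last covariate to be included in matching and adjustment is Elixhauser Comorbidity Measure (ECM". Its form is "at the year of KA, categorized into 3: 0, 1-2 and" 3 or more. The section cites published sources for the measure but gives no version, item list or exclusion.
- **Propensity score (Statistical Methods).** "propensity scores will be calculated based on age in years, female sex, completed education, household income, comedications, and ECM". The score is used in "propensity adjusted models using inverse probability of treatment weighting (IPTW", beside a crude Cox model.
- **Decision rule (Statistical Methods).** Absence of an important excess risk "will be established if the upper bound of the 95% confidence interval for the hazard ratio remains below 1.5". The text does not say whether this is the crude or the weighted hazard ratio.
- **Where the score is used.** The ECM is a row in the Table 1 mock-up. The adjusted halves of Table 2 and of sensitivity analysis tables 1 and 3 depend on it through the weights.

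**The concern.** A comorbidity count used to balance obese and non-obese patients should not itself count obesity. Suppose the version used gives a point for an obesity diagnosis. An obese patient with that code and no other disease then moves from ECM 0 to ECM 1-2, whereas a non-obese patient gets there essentially only by having another disease. Within ECM 1-2 and within 3 or more, the obese are then the healthier group on everything else. Weighting on those categories compares them with sicker non-obese patients, which lowers the adjusted hazard ratio if the other diseases raise PJI risk. The Introduction supports that condition: it lists diabetes, rheumatoid arthritis and depression among the factors linked to PJI.

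A lower adjusted hazard ratio makes an upper bound below 1.5 easier to reach, if the rule is applied to that estimate. It could also affect which morbid-obesity comparison is run, because the Sensitivity analyses section makes that choice depend on whether a difference was found. In Table 1, the standardized difference for ECM would partly reflect the exposure.

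The point concerns what the score contains, not the time window over which it is collected.

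**Working it through.** **The plan's own figure.** A 50% increase on a 2-year incidence of 1% gives HR = ln(1 − 0.015) / ln(1 − 0.010) = 1.504. The stated margin of 1.5 reproduces. The plan gives no figure for obesity coding, comorbidity by group, or comorbidity effect, so all inputs below are assumptions.

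**Model.** 40% obese; number of other comorbidities Poisson with mean 0.8 in both groups; PJI risk multiplied by r per other comorbidity; true obesity ratio 1.50; obesity coded in 0.5% of the non-obese and in a fraction c of the obese. With ECM as the only covariate, inverse probability weighting standardises both groups to the pooled ECM distribution:

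ratio = Σ T(l)·R1(l) / Σ T(l)·R0(l)

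T(l) is the pooled share in ECM category l. R1 and R0 are the mean relative risks of obese and non-obese patients in that category. At about 1% incidence the risk ratio approximates the hazard ratio.

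**One case in full: c = 30%, r = 1.3, obesity item kept.** Poisson shares for 0, 1, 2 and 3+ comorbidities are 0.4493, 0.3595, 0.1438 and 0.0474.

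- ECM 0: obese 0.7 × 0.4493 = 0.3145; non-obese 0.995 × 0.4493 = 0.4471.
- ECM 1-2: obese 0.7 × (0.3595 + 0.1438) + 0.3 × (0.4493 + 0.3595) = 0.5949; non-obese, with 0.995 and 0.005, 0.5048.
- ECM 3+: the remainders, 0.0906 and 0.0481.
- Mean number of other comorbidities within ECM 1-2: obese 0.94, non-obese 1.28. This gap is the mechanism.

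| ECM | T | R1 | R0 | R1/R0 |
|---|---|---|---|---|
| 0 | 0.3941 | 1.500 | 1.000 | 1.50 |
| 1-2 | 0.5408 | 1.947 | 1.409 | 1.38 |
| 3+ | 0.0651 | 3.056 | 2.344 | 1.30 |

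Obese: 0.3941 × 1.500 + 0.5408 × 1.947 + 0.0651 × 3.056 = 1.843. Non-obese: 0.3941 × 1.000 + 0.5408 × 1.409 + 0.0651 × 2.344 = 1.309. Ratio 1.843 / 1.309 = 1.41, which is 6% below 1.50.

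**The same calculation over a range, item kept:**

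| Obese patients coded | r = 1.0 | r = 1.2 | r = 1.3 | r = 1.5 |
|---|---|---|---|---|
| 2% | 1.50 | 1.50 | 1.49 | 1.49 |
| 5% | 1.50 | 1.49 | 1.48 | 1.47 |
| 10% | 1.50 | 1.48 | 1.47 | 1.45 |
| 30% | 1.50 | 1.44 | 1.41 | 1.35 |
| 50% | 1.50 | 1.40 | 1.36 | 1.28 |

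With the item removed, every cell is 1.50. That result depends on both groups having the same mean comorbidity.

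**If the obese have more comorbidity (r = 1.3).** With an obese mean of 1.0 or 1.2 against 0.8, the score without the item gives 1.515 or 1.530, because three coarse categories leave some confounding. With the item kept, the result is 1.500 (mean 1.0, 5% coded) or 1.503 (mean 1.2, 10% coded). At sparse coding the two errors can cancel.

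**A second model, with coding linked to severity.** Assumptions: 30-50% obese; 30% of the obese severely so; 2-30% of mild and 10-80% of severe obesity coded. With r of 1.2-1.4, the hazard ratio with the item kept is 0.89 to 0.99 times that with it removed. With r = 1.0 the factor is 1.00, unless coding concentrates in severe obesity and severe obesity carries a larger effect (then 0.98 to 0.99). In the one case run at r = 0.9 the direction reverses, to 1.518 / 1.497 = 1.01.

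**Limiting case.** If every obese patient were coded, none would have ECM 0, and the weights could not be formed.

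**The case against.** The strongest reply is that the documents never list the ECM items. A reader might infer that the measure certainly counts obesity, but that rests on the content of a cited source and not on the plan. This stands, so the point has to be conditional. What remains is that the plan leaves the question open in a study whose exposure is obesity.

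A reader might also infer that the exposure is adjusted for itself. That is too strong. Exposure is BMI from registered height and weight, BMI is not in the propensity score, and at most one diagnosis-coded point enters a three-level count. The overlap depends on how often hospitals code obesity, which the plan does not say.

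Nor is the downward pull certain. It is negligible at 2% coding and nil in the first model when comorbidity does not affect PJI. With sparse coding and a more comorbid obese group, removing the item need not bring the estimate closer to the truth. That is chance cancellation of two errors, though, and no reason to keep the item. Both models also omit the other propensity-score covariates; glucose-lowering and antithrombotic drugs carry some of the same comorbidity information and may shrink the effect.

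Finally, a reader might infer that the 1.5 rule is compromised. The plan does not tie the rule to the adjusted hazard ratio, and the crude one, reported alongside, does not use the ECM. A gap between the two would be visible, but its cause would not.

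**Conclusion.** The concern holds in conditional form. The plan puts the ECM into the propensity score for obesity and excludes no obesity or weight item. If the version used counts an obesity diagnosis, part of the exposure enters its own adjustment set, and the adjusted hazard ratio is likely pulled downward when other comorbidities raise PJI risk.

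The size rests wholly on assumptions. With a true ratio of 1.50, the fall is nil when comorbidity has no effect. At ×1.3 per comorbidity it is under 1% with 2% of obese patients coded, about 1% with 5% and about 6% with 30%. With 50% coded it is about 9% at ×1.3 and 15% at ×1.5. It would favour an upper bound below 1.5 only if the rule is read on the adjusted estimate. No figure in the plan is shown to be wrong. This is something that should be fixed because the repair is nearly free, and it does not by itself invalidate the analysis.

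**What to change.** In Covariates, state that the ECM is computed without any obesity or weight item, and name the version and items used. Use that score in Table 1, in the propensity score behind the adjusted part of Table 2, and in sensitivity analysis tables 1 and 3. It would help to say in the same edit, under Statistical Methods, which hazard ratio the 1.5 rule applies to.

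The cost is a sentence or two and one line of code, with no new data. The score is then no longer the full published measure, which needs a footnote. If the chosen version has no such item, saying so closes the point and no result changes.

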## INTRODUCTION

Knee arthroplasty are effective treatments of end-stage joint disease not responding to other treatment measures. Periprosthetic Joint infection (PJI) is an unusual but devastating complication of joint arthroplasty. It carries significant burden on patients' morbidity in terms of severe pain, decreased physical activity and quality of life and may lead to death. The microbial profile of PJI significantly influences treatment outcomes, with Gram-negative bacteria (GNB), including multidrug-resistant (MDR) pathogens having highest rate of failures. coagulase negative staphylococcus was also found to experience a high risk of re-revision. Studies have linked increasing body mass index (BMI), smoking, male gender, diabetes, rheumatoid arthritis, depression, history of steroid use and previous joint surgery with an increased risk of PJI after Total Knee Arthroplasty (TKA); from these, increasing BMI is found to be the most consistent risk factor for developing PJI.

Theories to understand and by that prevent PJI in overweight and obese patients have been proposed; under-dosed prophylactic antibiotics, increased surface tension, increased blood glucose and increased bacterial colonization of the skin in the groin are possible explanations of the association between PJI and overweight. A previous study showed that obese patients have higher rates of polymicrobial and Gram-negative early periprosthetic joint infections of the hip than non-obese patients. This study looked however only in early infections treated with debridement, antibiotics and implant retention (DAIR). A single previous cohort study from England and Wales found that the mean BMI was higher in Mixed genus PJI. We anticipate that knowing the microbial profile in obese patients can help in choosing the proper prophylactic measures for this group as well as tailoring the empirical antibiotics in relation to PJI in obese patients.

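### Apart from drug proxies, comorbidity enters the propensity score as one three-level category, which can leave a modest, avoidable bias of unknown direction in the adjusted hazard ratio

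*Combined protocol and SAP*

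**What the plan says.** Statistical Methods plans "propensity adjusted models using inverse probability of treatment weighting (IPTW" and gives the contents of the score: "propensity scores will be calculated based on age in years, female sex, completed education, household income, comedications, and ECM".

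Covariates enters the ECM "at the year of KA, categorized into 3: 0, 1-2 and" ≥3, and mock Table 1 shows the same three levels. The plan calls it a measure that scores comorbidity ("ECM is validated comorbidity scoring measure"). It does not list the conditions or say whether they are weighted. A plain count is the natural reading of 0, 1-2 and ≥3, but it is not stated.

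Comedications also carry disease information. One is justified by diabetes: "1) Glucose-lowering due to the association between DM and surgical complications". Others are justified by bleeding: "2) Antithrombotic medications and 3) NSAIDs because of the possible postoperative bleeding-related complications". Antiresorptives are justified by revision risk. Antibiotics appear in the look-back wording and in mock Table 1.

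The Introduction names "diabetes, rheumatoid arthritis, depression" among the factors linked to infection after knee arthroplasty. Diabetes has a drug proxy in the score. Rheumatoid arthritis and depression have no term of their own. The Sensitivity analyses section contains no alternative specification of comorbidity, and the mock tables show balance for the three ECM levels only.

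**The concern.** Weighting on a three-level category makes the share of patients in each level equal between the groups. It does not make the diseases within a level equal. If obese and non-obese patients reach level 1-2 through different conditions, and those conditions carry different PJI risks, the weighted groups still differ in baseline risk.

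This matters because the plan will conclude that there is no clinically meaningful increase if the upper 95% limit of the hazard ratio is below 1.5. A few percent of bias can matter when that limit lies close to the margin. The confidence interval does not reflect this error, and the planned tables would not reveal it.

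**Working it through.** **The plan's own figure.** The plan equates a 50% increase over a 2-year incidence of 1% with a hazard ratio of 1.5. Check: ln(1 − 0.015) / ln(1 − 0.01) = 1.504. It reproduces.

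**Inputs.** From the plan: the three levels, inverse probability weighting, incidence of about 1%, margin 1.5. The plan gives no group split, disease prevalences, disease effects or event count, so these are assumptions: 40% obese, conditions independent within each group, risks multiplicative. At 1% incidence the risk ratio is close to the hazard ratio. The true hazard ratio is set to 1.00 in steps 1 to 5, so any departure is bias in proportional terms.

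**Step 1, same disease mix in both groups.** Crude 1.00, category-weighted 1.00. Coarse grouping alone causes no bias.

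**Step 2, a worked example of a downward pull.** A condition with risk ratio 2 affects 20% of both groups. A harmless condition affects 50% of obese and 20% of non-obese patients. Crude is 1.00.
- Level 0: obese 0.8 × 0.5 = 0.40; non-obese 0.8 × 0.8 = 0.64; all patients 0.4 × 0.40 + 0.6 × 0.64 = 0.544. Level 1-2 holds the other 0.456.
- Mean relative risk in level 1-2: obese (0.2 × 2 + 0.8 × 0.5) / 0.60 = 1.333; non-obese (0.2 × 2 + 0.8 × 0.2) / 0.36 = 1.556.
- Weighted ratio: (0.544 + 0.456 × 1.333) / (0.544 + 0.456 × 1.556) = 1.152 / 1.253 = 0.919.

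This mix is extreme. If a comedication covariate fully captures the high-risk condition, the result returns to 1.00.

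**Step 3, the opposite direction.** With the harmless condition at 10% in obese and 40% in non-obese patients, level 0 holds 0.4 × 0.72 + 0.6 × 0.48 = 0.576. The level 1-2 means are 0.48 / 0.28 = 1.714 and 0.72 / 0.52 = 1.385. The ratio is (0.576 + 0.424 × 1.714) / (0.576 + 0.424 × 1.385) = 1.303 / 1.163 = 1.12, an upward pull.

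**Step 4, milder mixes.** One common condition affects 45% of the non-obese, with an odds ratio of 1.5 to 2.5 for obesity. Five others affect 4% to 10% each, with PJI hazard ratios of 1.3 to 2.0.

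| Assumption | Crude | Category-weighted | Individual conditions |
|---|---|---|---|
| Common condition harmless, others unrelated to obesity | 1.00 | 0.96 to 0.98 | 1.00 |
| Common condition has PJI hazard ratio 1.1 to 1.3, others commoner in the obese (odds ratio 1.2) | 1.04 to 1.09 | 0.99 to 1.01 | 1.00 |

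These rows spread the five hazard ratios across 1.3 to 2.0. If all five are 2.0 and the odds ratio is 2.5, the first row falls to 0.93. The last column equals the truth by construction, because every risk condition in the scenarios is measured.

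**Step 5, adding a diabetes drug proxy.** Diabetes affects 10% of the non-obese (odds ratio 2.5, PJI risk ratio 1.5), and 85% of it is captured by drugs. The harmless 45% condition stays, with four uncaptured conditions at 4% to 10% (risk ratio 1.3 to 2.0, unrelated to obesity). Crude is 1.06; category plus drug proxy gives 0.94 to 1.00. The lower end again needs all four at 2.0. The proxy helps only for the disease it captures.

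**Step 6, effect on the decision.** Assume a true hazard ratio of 1.5 and 400 to 800 events (40,000 to 80,000 operations at 1%). SE ≈ 1 / √(events × 0.4 × 0.6) = 0.102 or 0.072, ignoring the effect of weighting on the variance. Without bias, the upper limit falls below 1.5 with probability 2.5%. With a downward bias of 2% or 4% (0.020 or 0.041 on the log scale) the probability is Φ(−1.96 + bias / SE):
- 400 events: Φ(−1.76) = 3.9% and Φ(−1.56) = 5.9%.
- 800 events: Φ(−1.68) = 4.6% and Φ(−1.40) = 8.2%.

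**The case against.** A summary comorbidity score is a referenced and defensible choice, and the comedications add disease information. A reader might infer that comorbidity enters only as a count. That is wrong, because the drug covariates are in the score too, and a bias such as the one in step 2 disappears when a drug captures the risky condition. This stands, but only diabetes among the infection factors named in the Introduction has such a proxy.

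A reader might also infer that the adjustment pulls the hazard ratio towards a reassuring result, or makes it worse than the crude one. The documents do not support either. A downward pull requires that, within a level, the conditions of obese patients carry less PJI risk than those of non-obese patients. Nothing in the plan shows this, and diabetes is itself a named PJI risk factor. With plausible effects the category removes most of the confounding (step 4, second row).

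The cohort is limited to osteoarthritis, so rheumatoid arthritis as the reason for surgery is excluded. That makes it less common, but it does not exclude it as a coexisting diagnosis.

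Finally, the rule uses the upper limit, so a point estimate below 1.5 proves nothing by itself. For an estimate of 1.45 to have its upper limit below 1.5, SE must be ln(1.5 / 1.45) / 1.96 = 0.0173, or about 13,900 events. That is right for an estimate sitting at its expected value. It leaves out sampling variation: step 6 shows that a small downward bias still raises the error rate at the margin.

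**Conclusion.** The point holds in a limited form. The planned score does not balance individual conditions other than through drug proxies, and it gives no term to two PJI risk factors that the plan itself names. The resulting bias is zero if the disease mix within levels is the same in both groups, and otherwise can go either way. Under the milder assumptions it is about 0 to 4%; more extreme mixes give more, such as 0.92 and 1.12 in steps 2 and 3. If it happened to be 2 to 4% downward, a false conclusion at a true hazard ratio of 1.5 would become about 4 to 8% likely instead of 2.5%, given 400 to 800 events.

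All prevalences, effects and event counts here are assumptions, and so is the reading of the ECM as an unweighted count. The category usually still improves on the crude estimate. The change is worth considering, mainly because it is cheap and corrects imbalance in measured conditions in either direction.

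**What to change.** In Covariates and Statistical Methods:
- List the ECM conditions and the scoring. If an item records obesity itself, leave it out of the score, since it is the exposure.
- Enter the component conditions in the propensity score as separate yes/no indicators, with rare ones pooled.
- Give rheumatoid arthritis and depression their own terms, whether or not they are ECM items.
- Keep the 0, 1-2, ≥3 category for Table 1, and use it in the propensity score as a sensitivity analysis.
- Report standardized differences after weighting for each condition.

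The cost is mostly wording. Indicators for the component conditions are needed to build the ECM in any case; rheumatoid arthritis and depression need extra coding only if they are not among them. The downside is a larger propensity model, so the plan should add a check for extreme weights.

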**Planned Statistical Analyses:** We will use descriptive statistics to summarize the baseline characteristics of the two groups. Hazard ratios with corresponding two-sided 95% confidence intervals (95%CIs) for experiencing the outcome will be estimated using a Cox proportional hazards regression model. We will fit both unadjusted (crude) model and a propensity score adjusted model calculated based on age, sex, highest completed education, household income, comedication, and Elixhauser Comorbidity Measure (ECM), all collected up to the day of surgery. Stratified analyses will categorize PJI cases by bacterial infection and compare crude proportions between groups based on the absolute risk difference with 95% confidence intervals.

**Ethical Considerations and Registration:** The study and its statistical analysis plan will be registered in clinicaltrials.org prior to conducting the study.

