## Data sources

The Danish Civil Registration System (DCRS) contains information on the CPR number, vital and migrant status, cohabiting status, and municipality of residence. The Danish Knee Arthroplasty Register (DKR) is nation-wide register that contains information on all primary knee arthroplasty procedures and revisions performed in Denmark, e.g., baseline characteristics as age, sex, BMI, at the time of TKA operation. The registry started in 1997 and the reporting to the registry became mandatory since 2006. DKR is known for high degree of coverage and completeness. The Danish Microbiology Database (MiBa) is a national database containing data from all samples received by the Danish clinical microbiology departments from both hospitals and general practices with complete coverage since 2010.

The Danish National Patient Register (DNPR) is a valuable tool for epidemiological research, providing longitudinal registration of diagnoses, treatments, and examinations derived from every hospital contact in Denmark with complete nationwide coverage since 1978. The Danish National Prescription Registry has kept information on all prescriptions for drugs dispensed by community pharmacies in Denmark since 1994 according to Anatomical Therapeutic Chemical (ATC) classification system (ATC codes). Data from the Danish National Prescription Registry does not include hospital dispensaries.

The Danish Registers on Personal Income and Transfer Payments contains more than 160 variables including salaries, entrepreneurial income, taxes, public transfer payments, capital income, private pension contributions, and pay-outs. In addition, Statistics Denmark provide more detailed registers on specific income transfers, including sickness benefit, old age pension, disability pension, and cash and unemployment benefits. The Danish Population Education Register provides information on education status on Danish population, and it carries high degree of validity and coverage.

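### The ECM is dated to the year of surgery with no look-back length; cut at surgery, this gives 0 to 12 months of history by operation date and can leave residual confounding in the adjusted hazard ratio

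*Combined protocol and SAP*

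**What the plan says.** The Covariates section introduces its list with "we will be using the following pre-TKA exposure covariates" and then dates the items in three different ways:

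- Income: "household income (at the year before KA, categorized into quartiles".
- Comedication: "at least one redeemed prescription 365 days earlier to index KA - 60 days for antibiotics".
- ECM: "at the year of KA, categorized into 3: 0, 1-2" and three or more. Education carries the same year-of-surgery dating.

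No start date, end date, look-back length or diagnosis source is given for the ECM.

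Statistical Methods lists the propensity score items, ending with "comedications, and ECM (all collected prior to surgery". The Summary (Planned Statistical Analyses) says of the same items "all collected up to the day of surgery". The propensity score supplies the inverse probability weights for the adjusted Cox hazard ratio. Statistical Methods judges a hazard ratio against 1.5: a relevant increase is ruled out if the upper 95% confidence limit lies below that value.

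Data sources describes the DNPR as holding diagnoses from hospital contacts, "with complete nationwide coverage since 1978", but does not name it as the source of the ECM.

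**The concern.** The section distinguishes the year of surgery from the year before it, and it counts days where it wants a rolling window. Dating the ECM to the year of surgery therefore reads most naturally as the calendar year. That phrase has to be squared with three statements that the covariates are pre-operative. The obvious way is to start on 1 January and stop at the operation.

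This obeys every statement but gives an uneven covariate. Someone operated on 20 January has 19 days of history before surgery, and someone operated on 20 December has 353. With the same illnesses, the first is far more likely to fall in ECM category 0. Weighting then balances recorded comorbidity, and part of the true difference between obese and non-obese patients stays in the adjusted hazard ratio.

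The ECM is the plan's only general measure of comorbidity in the propensity score, so how well it is measured matters for the adjusted primary result.

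**Working it through.** **Plan's own figures.** The documents give no look-back length, sample size or event count, so there is no design figure to reproduce on this point. The one related figure checks out: a rise in 2-year risk from 1% to 1.5% gives HR = ln(1 − 0.015)/ln(1 − 0.01) = 1.504, in line with the stated 1.5.

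**Look-back under the truncated calendar year.** Assumption: surgery dates are spread evenly over the year. Look-back is then uniform on 0 to 365 days.

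- Mean: 365/2 = 182.5 days.
- Under 30 days: 30/365 = 8.2%.
- Under 90 days: 90/365 = 24.7%.

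**What this does to recording.** Assume that each true comorbidity is recorded at a constant rate of 1.19 per year (0.7 × 1.7). The probability of being seen in d days is 1 − exp(−1.19 d/365).

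- Fixed 365 days: 1 − exp(−1.19) = 0.70.
- 90 days: 1 − exp(−0.293) = 0.25.
- Average over the uniform look-back: 1 − (1 − exp(−1.19))/1.19 = 1 − 0.696/1.19 = 0.42.

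On this assumption the truncated window captures about 42% of comorbidities, against 70% for a fixed year.

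**Effect on the hazard ratio (illustrative).** A simulation used 4 million patients per scenario and the recording rate above. All inputs are assumptions: 45% obese; true HR 1.5; half of infections within 90 days; mean comorbidity count 1.2 or 1.5 times higher in obese patients; HR 1.2 or 1.4 per comorbidity. The weights used the ECM alone, in the plan's three categories. The HR was taken from weighted cumulative hazards.

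| Comorbidity ratio, HR per comorbidity | Crude | Calendar year cut at surgery | Fixed 365 days | Difference |
|---|---|---|---|---|
| 1.2, 1.2 | 1.558 | 1.537 | 1.520 | 0.017 |
| 1.2, 1.4 | 1.609 | 1.568 | 1.536 | 0.032 |
| 1.5, 1.2 | 1.643 | 1.594 | 1.548 | 0.046 |
| 1.5, 1.4 | 1.812 | 1.703 | 1.615 | 0.088 |

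Weighting on the true comorbidity count gave 1.49 to 1.50. In all four scenarios the truncated window lies between the fixed window and the crude value. A fixed year also leaves some confounding (1.52 to 1.62), which argues for a window longer than 12 months.

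**The case against.** **The phrase can be read in a sound way.** It could mean the 365 days before surgery, as for comedication, or all recorded history up to surgery. Either would exclude post-operative codes and remove the dependence on operation date. This stands: the truncated calendar year is the most natural reading, not the only one. But the section words a 365-day window differently where it wants one, and no statement in the plan fixes the start of the ECM window. The choice would fall to whoever programs the variable.

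**Operation date has no stated link to obesity.** This also stands. Uneven look-back does not by itself create a difference between the groups; it weakens control of confounding that already exists.

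**A reader might infer that the score counts diagnoses made after surgery, including those recorded at an infection admission.** Taken literally, the whole calendar year would cover on average 182.5/730 = 25% of follow-up and about 88% of the first 90 days (1 − 45/365). The documents do not support this as the plan. Covariates, Statistical Methods and the Summary each place the covariates before or up to surgery, and the Table 1 mock-up presents the ECM as a baseline characteristic. It remains only a risk of literal programming. If infection admissions then added codes, the same simulation gave hazard ratios from 1.22 to 1.55, depending on how much extra coding is assumed. That range does not describe the planned analysis.

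**A reader might also extend the point to education, which carries the same dating.** The documents give no reason to think that highest completed education changes because of surgery or infection.

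**Conclusion.** The ECM window is not defined. The year-of-surgery dating fits poorly with the statements that covariates are pre-operative, and the most natural way to reconcile them gives a weaker confounder than the plan needs. With evenly spread surgery dates, about a quarter of patients would have under 90 days of look-back. The expected consequence is residual confounding that moves the adjusted hazard ratio towards the crude one. The size cannot be known from the documents; 0.02 to 0.09 on the hazard ratio scale rests wholly on the assumed inputs.

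A reader might infer that this favours a false finding of no relevant increase. The documents do not support that. If obese patients carry more comorbidity and comorbidity raises infection risk, as assumed above, the truncated window pushes the hazard ratio up, which makes the rule of an upper limit below 1.5 harder to meet. Nor is it shown that the primary analysis is biased: a sound reading of the phrase exists. This is a cheap improvement.

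**What to change.** In Covariates, replace the year-of-surgery dating of the ECM with one look-back of fixed length in days or years, the same for every patient, ending the day before the index admission, and name the DNPR as the source. Five years would serve as an example: for the earliest surgery in 2011 it reaches back to 2006, well inside the register's stated coverage since 1978. Use the same end point in Statistical Methods and the Summary, so that all three places agree.

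The cost is one sentence in the SAP and a date filter in the program.
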